2.1.2 Reagents

In-vitro artificial aqueous humor:

AHA is prepared by dissolving NaCl (6.19 g/L), KCl (0.39 g/L), CaCl₂ (0.28 g/L), NaHCO₃ (2.90

g/L), glucose (0.80 g/L), Urea (0.10 g/L), albumin (0.10 g/L), Na-lactate (0.28 g/L) and Na-ascorbate (0.15 g/L) in water. Each substance is added separately in the above mentioned order. The solution is to be stirred constantly and kept at room temperature. Na-lactate and Na -ascorbate are added last and the solution is then adjusted at pH 7.21 with HCl 1M. Aqueous humor is centrifuge at 4000 rpm for 1 minute, supernatant is stored at 4°C until

analysis.

1M HCOONH₄:

Weight 6.6 g of HCOONH4 and transfer in a 100 mL graduated flask, then

dilute with H₂O to volume.

Code: GCLP022/01

Page. 12 of 27

10 mM HCOONH₄:

10 mL of 1M HCOONH4 are diluted to 1 L with water

2.1.3 Hazard and Precautionary statements

Acetonitrile:

H225, H302 + H332 + H312, H319

P210, P280, P305 + P351 + P338

Methanol:

H225, H303 + H311 + H331, H370

P210, P260, P280, P301 + P310, P311

Ammonium acetate: n/a

Formic acid:

H226, H314

P280, P305 + P351 + P338, P310

2.2 DETERMINATION BY LC-MS/MS

2.2.1 Instrument

HPLC:

Agilent 1260 Infinity Series

Detector:

ABSciexAPI-4500 Triple Quadrupole

Data system:

Analyst ver. 1.6

2.2.2 Chromatographic conditions

Column:

Thermo Fisher HYPERSYL GOLD C 50x3mm, 3µm

Mobile phase A:

1 L 10 mM ammonium formiate + 1 mL formic acid

Mobile phase B:

500 mL Acetonitrile + 500 mL Methanol + 1 mL formic acid

Needle wash:

50 mL iso-Propanol + 450 mL Acetonitrile + 500 mL Methanol

+1 mL formic acid

Elution mode:

gradient

Time (min)	A %	B%	
0	90	10	
6	0	100	
9	0	100	
9.5	90	10	
15	90	10	

Flow rate:

0.7 mL/min

Code: GCLP022/01

Page. 13 of 27

Column temperature:

Nominally 40°C

Injection volume:

 $2 \mu L$

Autosampler temperature: Nominally at 10°C

2.2.3 Mass-Spectrometry conditions

Source:

Turbo Ion Spray (Positive Polarity)

Source temperature:

500°C

Con Voltage:

5500 eV

Desolvation / nebulizer gas: 50/50

Divert Valve to source:

from 0.5 minutes to 6 minutes

Ions Monitored:

MRM

ID	Q1 mass	Q3 mass	CE	Dwell time (msec)
	amu	amu		***************************************
Levofloxacin	362.1	261.0	40	90
Levofloxacin *	362.1	318.0	30	90
Dexamethasone	393.2	373.1	15	90
Dexamethasone*	393.2	355.0	15	90
Dexamethasone 21-phosphate	473.1	435.1	18	90
Dexamethasone 21-phosphate*	473.1	355.0	18	90
Progesterone	315.10	109.0	50	90
Progesterone*	315.10	297.1	35	90

^{*} for qualitative use

Instrument parameters may be adjusted, according to the instrument changes over the time.

2.3 STANDARD SOLUTIONS

2.3.1 Stock and working standard solutions for calibration sample.

Levofloxacin Stock Standard Solution-1

Weigh accurately about 10 mg of Levofloxacin into a 10 mL volumetric flask, dissolve with methanol then dilute to volume with the same solvent and mix. The concentration of this solution is $2.767 \, \mu mol/mL$.

Code: GCLP022/01

Page. 14 of 27

Dexamethasone 21-phosphate Stock Standard Solution-1

Weigh accurately about 10 mg of Dexamethasone sodium 21-phosphate into a 10 mL volumetric flask, dissolve with water/methanol 50/50 (v/v) then dilute to volume with the same solvent and mix. The concentration of this solution is 1.936 µmol/mL of Dexamethasone 21-phosphate.

Dexamethasone Stock Standard Solution-1

Weigh accurately about 10 mg of Dexamethasone into a 10 mL volumetric flask, dissolve with water/methanol 50/50 (v/v) then dilute to volume with the same solvent and mix. The concentration of his solution is 2.548 µmol/mL.

Intermediate Standard Solution-1a

Transfer 1 mL of Levofloxacin and Dexamethasone Stock Standard Solution-1 into a 10 mL volumetric flask, then dilute to volume with water/methanol 50/50 (v/v) and mix. The concentration of this solution is 0.277 µmol/mL of Levofloxacin and 0.255 µmol/mL dexamethasone.

Intermediate Standard Solution-1b

Transfer 1 mL of Dexamethasone 21-phosphate Stock Standard Solution-1 into a 10 mL volumetric flask, then dilute to volume with water/methanol 50/50 (v/v) and mix. The concentration of this solution is 0.194 µmol/mL dexamethasone 21-phosphate.

Working Standard Solution A

Transfer 1 mL of Intermediate Standard Solution-1a and -1b in a 10 mL volumetric flask, then dilute to volume with water/methanol 50/50 (v/v) and mix.

Working Standard Solution B

Transfer 0.9 mL of Intermediate Standard Solution-1a and -1b in a 10 mL volumetric flask, then dilute to volume with water/methanol 50/50 (v/v) and mix.

Working Standard Solution C

Transfer 0.5 mL of Intermediate Standard Solution-1a and -1b in a 10 mL volumetric flask, then dilute to volume with water/methanol 50/50 (v/v) and mix.

Working Standard Solution D

Transfer 0.1 mL of Intermediate Standard Solution-1a and -1b in a 10 mL volumetric flask, then dilute to volume with water/methanol 50/50 (v/v) and mix.

Working Standard Solution E

Transfer 0.5 mL of Intermediate Standard Solution-1a and -1b in a 100 mL volumetric flask, then dilute to volume with water/methanol 50/50 (v/v) and mix.

Code: GCLP022/01

Page. 15 of 27

Working Standard Solution F

Transfer 0.1 mL of Intermediate Standard Solution-1a and 0.4 mL of Intermediate Standard Solution -1b in a 100 mL volumetric flask, then dilute to volume with water/methanol 50/50 (v/v) and mix.

Working Standard Solution G

Transfer 0.05 mL of Intermediate Standard Solution-1a and 0.3 mL of Intermediate Standard Solution-1b in a 100 mL volumetric flask, then dilute to volume with water/methanol 50/50 (v/v) and mix.

Store all the solutions at nominally 4°C.

2.3.2 Stock and working standard solutions for QC sample.

Levofloxacin Stock Standard Solution-2

Weigh accurately about 10 mg of Levofloxacin into a 10 mL volumetric flask, dissolve with methanol then dilute to volume with the same solvent and mix. The concentration of this solution is 2.767 µmol/mL.

Dexamethasone 21-phosphate Stock Standard Solution-2

Weigh accurately about 10 mg of Dexamethasone into a 10 mL volumetric flask, dissolve with water/methanol 50/50 (v/v) then dilute to volume with the same solvent and mix. The concentration of his solution is $2.548 \mu mol/mL$.

Dexamethasone Stock Standard Solution-2

Weigh accurately about 10 mg of Dexamethasone into a 10 mL volumetric flask, dissolve with water/methanol 50/50 (v/v) then dilute to volume with the same solvent and mix. The concentration of his solution is $2.548 \mu mol/mL$.

Intermediate Standard Solution-2a

Transfer 1 mL of Levofloxacin and Dexamethasone Stock Standard Solution-2 into a 10 mL volumetric flask, then dilute to volume with water/methanol 50/50 (v/v) and mix. The concentration of this solution is 0.277 µmol/mL of Levofloxacin and 0.255 µmol/mL dexamethasone.

Intermediate Standard Solution-2b

Transfer 1 mL of Dexamethasone 21-phosphate Stock Standard Solution-2 into a 10 mL volumetric flask, then dilute to volume with water/methanol 50/50 (v/v) and mix. The concentration of this solution is 0.194 µmol/mL dexamethasone 21-phosphate.

Code: GCLP022/01

Page. 16 of 27

Working Standard Solution H

Transfer 0.8 mL of Intermediate Standard Solution-2a and -2b in a 10 mL volumetric flask, then dilute to volume with water/methanol 50/50 (v/v) and mix.

Working Standard Solution I

Transfer 1 mL of Working Standard Solution H in a 10 mL volumetric flask, then dilute to volume with water/methanol 50/50 (v/v) and mix.

Working Standard Solution L

Transfer 0.15 mL of Intermediate Standard Solution-2a and 0.45 mL of Intermediate Standard Solution -1b in a 100 mL volumetric flask, then dilute to volume with water/methanol 50/50 (v/v) and mix.

Store all the solutions at nominally 4°C.

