2.4 BIOANALYTICALPROCEDURE

2.4.1 Preparation of calibration standard (CC) and quality control (QC) samples in artificial aqueous humor (AHA)

Use an seven-points calibration curve and three-level of QCs.

Prepare each calibration and QC sample by adding 1 mL of each Working Standard Solution from A to L to 9 mL of artificial aqueous humor (AHA), according to the following scheme:

Code: GCLP022/01

Page. 17 of 27

W	WS concentration (nmol/mL)		AHA concentration (nmol/mL)			ID	SAMPLE	
	Levo	DEX	DEX 21	Levo	DEX	DEX 21		
A	27.672	25.480	19.364	2.767	2.548	1.936	CC A	
В	24.905	22.932	17.428	2.491	2.293	1.743	CC B	
C	13.836	12.740	9.682	1.384	1.274	0.968	CCC	o !!!
D	2.767	2.548	1.936	0.277	0.255	0.194	CC D	Calibration
E	1.384	1.274	0.968	0.138	0.127	0.097	CCE	curve
F	0.277	0.255	0.775	0.028	0.025	0.078	CC F	
G	0.138	0.127	0.581	0.014	0.013	0.058	CC G	
Н	22.138	20.384	15.492	2.214	2.038	1.549	HQC	
I	2.214	2.038	1.549	0.221	0.204	0.155	MQC	QC
L	0.415	0.382	0.871	0.042	0.038	0.087	LQC	

where Levo is levofloxacin, DEX is dexamethasone and DEX 21-P is dexamethasone 21-phosphate

Divide each standard sample in AHA into 20 μ L aliquots, and store at nominally -80°C until analysis. Process calibration curve and QCs samples exactly as described in §2.4.2. Each calibration curve will include a blank sample (AHA sample processed without internal standard) and a zero blank sample (AHA sample processed with internal standard).

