4.6.1 Procedure

Analyze LQC level (blank matrix spiked with analytes after extraction) in matrix and at the same level (LQC) in absence of matrix (water/methanol 50/50 (v/v)). Repeat the analysis at HQC level. Using the same approach, Matrix effect is also evaluated in order to verify if oxibuprocaine² (use as anesthetic before the surgical procedure), iodopovidone (use as antimicrobial) and benzalkonium chloride (present in the drug product formulation) affect the determination. Oxibuprocaine, iodiopovidone and benzalkonium chloride levels that should be included in aqueous humor in order to define the matrix effect is defined according to literature. Mean values plus 2 times the standard deviation (SD) is tested.

Benzalkonium chloride (BAK) level found in rabbit aqueous humor after 15 drops of 0.05% BAC dosage [3] is $0.52 \pm 0.13 \,\mu\text{g/mL}$: Considering this value as mean \pm Standard Error (worst case) and being the study performed on 24 eyes, SD is 0.637^3 . According to this approach, BAK is tested at 1.8 $\,\mu\text{g/mL}$ in AHA. This is a worst case if compared to drug product posology in clinical study (2 drops of drug product containing 0.1 $\,\text{mg/mL}$ of BAK).

According to literature [4], lidocaine levels in human aqueous humor after administration of 3 and 6 drops of anesthetic at 4 mg/mL are $1.4 \pm 0.5 \,\mu\text{g/mL}$ and $4.2 \pm 1.5 \,\mu\text{g/mL}$ (Mean \pm SD) respectively. Assuming that the same absorption for oxibuprocaine, it is tested at 7.2 $\mu\text{g/mL}$ in AHA, worst case if compared to anesthetic posology (3 drops).

Iodopovidone (0.5% iodine) is used as antimicrobial and is not instilled inside the eye. It is tested at 7.2 μ g/mL in AHA, assuming an absorption similar to oxibuprocaine (worst case).

Prepare WS 1 containing 2.214 nmol/mL of levofloxacine, 2.038 nmol/mL dexamethasone,1.549 nmol/ mL of dexamethasone 21-phosphate and 1.59 nmol/mL of IS in methanol.

Prepare WS 2 containing 0.042 nmol/mL of levofloxacine, 0.038 nmol/mL dexamethasone, 0.087 nmol/ mL of dexamethasone 21-phosphate and 1.59 nmol/mL of IS in methanol.

Prepare LQC and HQC in solvent diluting 20 μ L of WS with 20 μ L of water (use WS1 for HQC and WS2 for LQC)

Prepare LQC and HQC in matrix (use WS1 for HQC and WS2 for LQC):

Matrix 1: 20 μ L of WS with 20 μ L of AHA

Matrix 2: 20 μL of WS with 20 μL of AHA containing BAK 0.8 μg/mL

² Lidocaine may be considered as backup, in case of oxibuprocaine matrix effect.

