4.8.1 Procedure

1. Dilute 800 μL of Intermediate Solution-2a and -2b (see § 2.3.2) to 10 mL of AHA.

Divide AHA samples into 10 μ L aliquots and use it to validate the dilution factor 1:10 (5 replicates each).

- 1:10 To 10 μ L aliquots add 90 μ L of blank AHA. The final concentration of analytes in in AHA is 2.214 nmol/mL of levofloxacin, 2.038 nmol mL of dexamethasone and 1.936 nmol/mL of dexamethasone 21-phosphate.
- 2. Dilute 800 µL of each Stock Standard Solution-2 (see § 2.3.2) to 10 mL of AHA.

Divide HA samples into 10μ L aliquots and use it to validate the dilution factor 1:100 (5 replicates each).

1:100 \rightarrow To 10 μ L aliquots add 90 μ L of blank AHA. Subsequently dilute 10 μ L of this diluted AHA sample with 90 μ L of blank AHA. The final concentration of analytes in in AHA 2.214 nmol/mL of levofloxacin, 2.038 nmol mL of dexamethasone and 1.936 nmol/mL of dexamethasone 21-phosphate.

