4.8.2 Calculation

Recalculate the concentration of AHA samples having a concentration higher than the ULOQ taking into account the dilution factor. Mean accuracy should be $\pm 15\%$ and precision (CV) should be $\leq 15\%$.

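### Laboratory protocol: the QC stock for dexamethasone 21-phosphate is made from the wrong substance, its dilution-integrity value should be 1.549 and not 1.936 nmol/mL, and its low QC draws on the calibration series

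*Combined protocol and SAP*

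**What the plan says.** All references are to the laboratory protocol in Appendix 12.1.

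- **Section 2.3.1 (calibration series).** The 21-phosphate Stock-1 is made from the phosphate salt: "Weigh accurately about 10 mg of Dexamethasone sodium 21-phosphate into a 10 mL volumetric flask". Its stated concentration is 1.936 µmol/mL.
- **Section 2.3.2 (QC series).** Under the heading for the 21-phosphate Stock-2 the instruction is "Weigh accurately about 10 mg of Dexamethasone into a 10 mL volumetric flask, dissolve with water/methanol 50/50 (v/v) then dilute to volume", with 2.548 µmol/mL. The same sentence is correct in the two places where it describes a dexamethasone stock (2.3.1, and the next entry in 2.3.2). Intermediate-2b then follows: "Transfer 1 mL of Dexamethasone 21-phosphate Stock Standard Solution-2 into a 10 mL volumetric flask", printed as 0.194 µmol/mL of 21-phosphate.
- **Section 2.3.2, Working Solution L (low QC).** "Transfer 0.15 mL of Intermediate Standard Solution-2a and 0.45 mL of Intermediate Standard Solution -1b in a 100 mL volumetric flask". Intermediate-1b belongs to the calibration series.
- **Section 2.4.1.** The table of seven calibrators and three QC levels gives 21-phosphate as 1.936 (top calibrator, CC A), 1.549 (HQC), 0.155 (MQC) and 0.087 nmol/mL (LQC).
- **Section 4.5.1.** QC samples are said to be prepared independently of the calibration standards.
- **Section 4.8.1 (dilution integrity).** Both arms start from 800 µL made to 10 mL. Both end at 2.214 nmol/mL of levofloxacin with "2.038 nmol mL of dexamethasone and 1.936 nmol/mL of dexamethasone 21-phosphate".
- **Section 4.6.1 (matrix effect).** The same levofloxacin and dexamethasone values appear with a different third figure: "Prepare WS 1 containing 2.214 nmol/mL of levofloxacine, 2.038 nmol/mL dexamethasone,1.549 nmol/ mL of dexamethasone 21-phosphate".

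**The concern.** Two printed figures conflict with the recipes they belong to, and one recipe conflicts with a statement of principle. The consequences are separate.

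If the Stock-2 recipe is followed, HQC and MQC lack one analyte and are overloaded with another. HQC is also used for recovery (4.7) and stability (4.9).

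If the printed dilution-integrity value is taken as nominal, a correct assay fails the test for 21-phosphate.

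If the low QC shares the calibration stock, an error in that stock moves calibrators and low QC together, so the low QC cannot reveal it for this analyte.

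The Synopsis lists dexamethasone 21-phosphate among the measured concentrations, and section 8.2 of the protocol relies on this appendix for the assay.

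**Working it through.** **Inputs.** Molecular weights (section 1.7.1): levofloxacin 361.37, dexamethasone 392.46, dexamethasone sodium phosphate 516.41 g/mol. Every stock is 10 mg in 10 mL, i.e. 1 mg/mL, so concentration in µmol/mL = 1000 / molecular weight. Each later step is volume taken / final volume. Spiking into artificial aqueous humour is 1 mL in 10 mL (2.4.1).

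**Reproducing the plan's figures.**
- Stocks: 1000/361.37 = 2.767; 1000/392.46 = 2.548; 1000/516.41 = 1.936 µmol/mL. These match 2.3.1.
- HQC with a phosphate-salt stock: 193.64 nmol/mL × 0.8/10 = 15.492, then /10 = 1.549 nmol/mL. MQC is one tenth, 0.155. Both match the 2.4.1 table.

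**(a) Stock-2.**
- As written, Intermediate-2b = 2.548/10 = 0.255 µmol/mL of dexamethasone. Printed: 0.194 of 21-phosphate.
- The printed value needs 1.936/10 = 0.194, the phosphate salt.
- Literal consequence: dexamethasone enters from both 2a and 2b. HQC = 2 × 254.80 × 0.8/100 = 4.077 nmol/mL against 2.038 nominal (+100%, and 4.077/2.548 = 1.60 times the top calibrator). MQC = 0.408 against 0.204. 21-phosphate is 0 against 1.549 and 0.155.
- Section 4.5.2 requires at least 50% of QCs at each level within 15% of nominal. An accurate assay would have 0 of 6 at HQC and 0 of 6 at MQC in the within-run test, for both analytes.

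**(b) Dilution integrity, Stock-2 taken as 1.936.**

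| Arm | Undiluted 21-phosphate (nmol/mL) | Final | Printed |
|---|---|---|---|
| 1:10, from Intermediate-2b | 193.64 × 0.8/10 = 15.49 | 1.549 | 1.936 |
| 1:100, from Stock-2 | 1936.4 × 0.8/10 = 154.9 | 1.549 | 1.936 |

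- The same volumes give levofloxacin 2.214 and dexamethasone 2.038 in both arms, as printed.
- Implied starting volumes: 2.214 × 100/276.72 = 0.800 mL; 2.038 × 100/254.80 = 0.800 mL; 1.936 × 100/193.64 = 1.000 mL. Only the 21-phosphate figure departs from 800 µL.
- No other reading rescues 1.936. The rounded 0.194 gives 1.552. Adding 800 µL to 10 mL (10.8 mL in all) gives 1.434 and also breaks the other two analytes. The printed 2.548 stock gives 2.038 in the 1:100 arm.
- If 1.936 is used as nominal: 1.549/1.936 − 1 = −20.0%, against ±15%. The ratio is the same undiluted (15.49/19.36 and 154.9/193.6). The limits would be 1.936 × 0.85 = 1.646 and 1.936 × 1.15 = 2.226, so only an assay reading 6.2% to 43.7% above 1.549 would pass.
- If the nominal is computed from the actual preparation, the error is 0%.

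**(c) Low QC.** 21-phosphate: 193.64 × 0.45/1000 = 0.087; dexamethasone: 254.80 × 0.15/1000 = 0.038 nmol/mL. Both match the table. Only the source conflicts with 4.5.1.

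**The case against.** The arithmetic is not in dispute; the case against is about weight.

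- **Stock-2 is a self-revealing copy slip.** The heading, the Intermediate-2b line, the Stock-1 recipe and the 2.4.1 table all point to the phosphate salt, and a literal preparation would fail visibly. This stands, and it keeps the point minor. It does not make the text acceptable: section 1.4 has the Study Director work to this protocol and justify deviations, so quietly preparing the right stock would itself be a deviation.
- **The −20% is conditional.** Stocks are weighed to about 10 mg, section 4.5.2 divides by actual concentration, and section 4.8.2 works at the undiluted level ("Recalculate the concentration of AHA samples having a concentration higher than the ULOQ taking into account the dilution factor"), for which no nominal is printed. A laboratory using its own weighings and volumes sees no error. This stands as a limit on the consequence, although Table 1 sets the criterion against nominal. The printed 1.936 is wrong either way.
- **The low-QC point is interpretation.** Section 4.5.1 does not expressly demand separate stocks, and LQC is not made from any calibration sample. That is fair, so it is listed as an inconsistency with a statement and not as a wrong figure. The separate -1 and -2 series make separate stocks the natural reading.
- **There is no route to the trial endpoint.** Study samples are read from the calibration curve (section 3), whose Stock-1 recipe is correct. Agreed; no bias is claimed.

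**Conclusion.** The concern holds and is minor. Two entries contradict the document's own figures: the 21-phosphate Stock-2 recipe (0.255 µmol/mL of dexamethasone where 0.194 of 21-phosphate is printed for Intermediate-2b) and the dilution-integrity concentration (1.936 printed, 1.549 nmol/mL obtained, in both arms). One entry, the source of the low QC's 21-phosphate, is inconsistent with the independence statement and changes no value.

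The failure scenarios are alternatives and do not add up. The one under (a) assumes the recipe is followed literally. The −20.0% under (b) assumes Stock-2 is corrected and the printed figure is used as nominal. Under (c), LQC loses its role as an independent check for one analyte; once Stock-2 is corrected, MQC and HQC still provide that check. Confidence is high, since every step uses printed weights, volumes and molecular weights. Sample size and the planned analysis are unaffected.

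**What to change.** Before validation is run, make four text edits in Appendix 12.1:

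1. Section 2.3.2, 21-phosphate Stock-2: name dexamethasone sodium 21-phosphate as the substance weighed and give 1.936 µmol/mL.
2. Section 2.3.2, Working Solution L: replace Intermediate-1b with Intermediate-2b.
3. and 4. Section 4.8.1: change 1.936 to 1.549 nmol/mL for 21-phosphate in each arm. It would help to print the undiluted nominals that section 4.8.2 needs as well (15.49 and 154.9 nmol/mL).

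Edits 1 and 2 must go together. With only Solution L changed, LQC would hold no 21-phosphate and 254.80 × (0.15 + 0.45)/1000 = 0.153 nmol/mL of dexamethasone in place of 0.038.

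The cost is the wording plus the amendment process in section 1.4 (sponsor authorisation, signatures of the Study Director and Sponsor Representative). Patients are not affected.

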2.3.3 Internal Standard solutions

IS Stock Standard Solution

Weigh accurately about 10 mg of Progesterone into a 10 mL volumetric flask, dissolve with methanol, then dilute to volume with the same solvent and mix.

IS Intermediate Standard Solution

Transfer 1 mL of IS Stock Standard Solution (1000 µg/mL) in a 100 mL volumetric flask, then dilute to volume with methanol and mix.

IS Working Standard Solution (1.590 nmol/mL)

Transfer 2.5 mL of IS Intermediate Standard Solution (10 μ g/mL) in a 50 mL volumetric flask, then dilute to volume with methanol and mix.

Store the solution at nominally 4°C.

2.4 BIOANALYTICALPROCEDURE

2.4.1 Preparation of calibration standard (CC) and quality control (QC) samples in artificial aqueous humor (AHA)

Use an seven-points calibration curve and three-level of QCs.

Prepare each calibration and QC sample by adding 1 mL of each Working Standard Solution from A to L to 9 mL of artificial aqueous humor (AHA), according to the following scheme:

Code: GCLP022/01

Page. 17 of 27

W	WS concentration (nmol/mL)		AHA concentration (nmol/mL)			ID	SAMPLE	
	Levo	DEX	DEX 21	Levo	DEX	DEX 21		
A	27.672	25.480	19.364	2.767	2.548	1.936	CC A	
В	24.905	22.932	17.428	2.491	2.293	1.743	CC B	
C	13.836	12.740	9.682	1.384	1.274	0.968	CCC	o !!!
D	2.767	2.548	1.936	0.277	0.255	0.194	CC D	Calibration
E	1.384	1.274	0.968	0.138	0.127	0.097	CCE	curve
F	0.277	0.255	0.775	0.028	0.025	0.078	CC F	
G	0.138	0.127	0.581	0.014	0.013	0.058	CC G	
Н	22.138	20.384	15.492	2.214	2.038	1.549	HQC	
I	2.214	2.038	1.549	0.221	0.204	0.155	MQC	QC
L	0.415	0.382	0.871	0.042	0.038	0.087	LQC	

where Levo is levofloxacin, DEX is dexamethasone and DEX 21-P is dexamethasone 21-phosphate

Divide each standard sample in AHA into 20 μ L aliquots, and store at nominally -80°C until analysis. Process calibration curve and QCs samples exactly as described in §2.4.2. Each calibration curve will include a blank sample (AHA sample processed without internal standard) and a zero blank sample (AHA sample processed with internal standard).

2.4.2 Sample preparation to analyse in AHA

Transfer 20 μL of AHA sample to a 1.5mL Eppendorf polypropylene tube; add 20 μL of the IS working standard solution and mix well by vortex for about 10sec. Centrifuge at 13000 rpm for 1 min at nominally 4°C, then transfer the supernatant in a autosampler plate and inject.

